6.3.6 Nonscalp Hair Growth

Starting at Week 8, subjects will be queried at each visit whether they have noticed any hair growth in nonscalp areas (yes/no) and this response will be captured in the eCRF. If judged by the investigator as clinically significant, nonscalp hair growth may be reported as an AE.

Examination Procedures, Tests, Equipment, and Techniques

All study photographs will be standardized for lighting, camera angle, and position of the subject's head Images will be uploaded to a secure website made available by the photography vendor, via flash drive or internet transfer. Detailed instructions for all aspects of the photography procedures will be supplied separately

6.4.1 Semipermanent Microdot Tattoo

For standardized photography, during the Day 1 (baseline) visit, subjects will receive two 1-mm semipermanent microdot tattoos

[figure not shown]
As the dots begins to fade or are at risk of fading before the next scheduled visit, they may be refreshed in the exact same locations.

6.4.2 Global Photographs

Two standardized global photographs (vertex target area and frontal area) will be taken at screening (the screening photograph is defined as the subject's baseline) and at Weeks 24, and 32 (or early exit visit). At Weeks 24, and 32 (or early exit visit), after refreshing the semipermanent microdot tattoo (if necessary) and parting and combing the hair radially away from the part, standardized global photographs of the subject's vertex target area will be presented in pairs (ie, 1 photograph taken at screening and the other photograph taken at a given treatment week

[figure not shown]

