2.2 Clinical Hypotheses

- Setipiprant tablets 1000 mg BID have an acceptable safety profile following oral administration for 24 weeks.
- Setipiprant tablets 1000 mg BID are more effective than placebo in increasing hair growth, as measured by the change from baseline in target area hair count (TAHC) of terminal hairs (1 cm² circular area) using digital image analysis at 24 weeks after oral administration.
- Setipiprant tablets 1000 mg BID are more effective than placebo in increasing scalp hair growth, as measured by the distribution of Subject Self-Assessment (SSA) scores using a 7-point scale at 24 weeks after oral administration.

3. Study Design

[figure not shown]
This is a multicenter, randomized, double-blind, placebo-controlled study with an active comparator group designed to determine the effect of treatment with setipiprant tablets 1000 mg BID on scalp hair growth as assessed by objective (ie, imaging-based) and subjective (ie, investigator- and subject-reported) measures.

All investigators, site staff, and subjects will be blinded to whether subjects receive setipiprant or matching placebo during the study.

Subjects must complete all screening and baseline procedures and meet all eligibility requirements to qualify for enrollment and randomization on Day 1 when they will be randomly

assigned to 1 of 2 treatment groups (setipiprant or placebo). All subjects will self-administer the assigned study drug over a 24 week period to evaluate the safety and effects on hair growth. After randomization, subjects will return to the research facility at Weeks 24 for protocol-defined efficacy and/or safety assessments and procedures, confirmation of compliance with study drug usage, and new study drug dispensation (except for Week 24). A follow-up visit will occur at Week 32 (ie, 8 weeks posttreatment) or the early exit visit for protocol-defined efficacy and safety evaluations and procedures.

Safety and efficacy assessments and study procedures are outlined in the Study Design and Schedule of Assessments (Table 1). The SSA will be evaluated at Weeks 24, and 32 (or early exit visit) using the subject's paired and randomly blinded screening (the screening photograph is defined as the subject's baseline) and postbaseline photographs, and at Weeks 24 and 32 (or early exit visit) using the subject's paired, unblinded screening and postbaseline photographs.

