5.3 Methods for Masking/Blinding

Evaluation of the setipiprant and placebo treatment groups will be conducted in a double-blind manner so that neither the site personnel nor the subject is aware of which treatment is administered. Both treatments will be identical in appearance

Except when it is essential for the medical management of the subject or bioanalytical reasons (ie, to enable bioanalysis of samples only from subjects who receive active treatment), unblinding the treatment assignment will be considered a protocol deviation. Instructions for access to emergency treatment allocation information will be available by secured access to the interactive web response system (IWRS). If possible, the investigator should contact the sponsor before unblinding any subject's treatment assignment. In the event that this is not possible, the sponsor must be notified within 24 hours after the unblinding event. After unblinding, the subject will be discontinued from study drug treatment and will return for a final follow-up (ie, Week 32 or early exit visit).

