6.1.1.1 Target Area Hair Count (Within a 1 cm² Circular Area)

[figure not shown]
One of the coprimary efficacy measures will be the subjects' TAHC as measured in terminal hairs (1 cm² circular area on the left side) using digital image analysis (A12.1.4).

The total number of terminal hairs (hair width \geq 30 µm) will be calculated from macrophotographs. The target area used to count TAHC will be a 1 cm² circular area of clipped hair (length approximately 1 mm) located at the anterior leading edge of the vertex thinning area of the scalp and centered with a semipermanent microdot tattoo to ensure the same target area is reproduced at each visit.

[figure not shown]

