6.1.1.2 Subject Self-Assessment

The SSA (A12.1.7) is a coprimary measure that consists of a single item that assesses each subject's perception of change in scalp hair growth. The subject uses a standardized global photograph of his scalp taken at the screening visit (the screening photograph is defined as the subject's baseline) presented side by side with a standardized global photograph taken at the postbaseline visit to give a comparative score. The photographs are presented in a blinded and randomized manner, and response options are on a 7-point ordinal scale. Refer to the imaging vendor manual for the methodology for obtaining global photographs.

[figure not shown]

[figure not shown]

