7.2.1 Primary Efficacy Variables

The 2 coprimary efficacy variables are based on the measurements of TAHC and SSA (blinded).

- Change from baseline in TAHC within a 1 cm² target circular area on the left side located at the anterior leading edge of the vertex thinning area of the scalp at Week 24
- Subject Self-Assessment of change from baseline in hair growth as viewed on the subject's paired (before and after presented in a blinded fashion) global photographs of the vertex target area at Week 24 and measured by the distribution of SSA scores

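### Do the Day 1 microdot tattoos give away photo order in the blinded Subject Self-Assessment?

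*Protocol*

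**What the plan says.** The SSA is one of two coprimary variables. Protocol 7.2.1 bases it on paired images, "before and after presented in a blinded fashion) global photographs of the vertex target area at Week 24". Under Protocol 6.1.1.2 the baseline image is the screening photograph, and the order of the two is masked and randomised. Protocol 7.2 and SAP 5.1.1.3.1 reverse the score when the later image happens to be Photo A.

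The tattoos come after that baseline image. Protocol 6.4.1 states that "during the Day 1 (baseline) visit, subjects will receive two 1-mm semipermanent microdot tattoos", and it allows them to be refreshed as they fade. Protocol 6.4.2 describes Weeks 24 and 32 in a sentence that begins "after refreshing the semipermanent microdot tattoo (if necessary) and parting and combing the hair radially away from the part, standardized global photographs" and goes on to the presentation of the pairs. One dot centres the hair-count target, which Protocol 6.1.1.1 describes as a "circular area of clipped hair (length approximately 1 mm) located at the anterior leading edge of the vertex thinning area of the scalp".

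The technical detail is kept elsewhere. Protocol 6.1.1.2 says "Refer to the imaging vendor manual for the methodology for obtaining global photographs", and the general paragraph on photography that follows Protocol 6.3.6 says "Detailed instructions for all aspects of the photography procedures will be supplied separately". A separate SSA, made "using the subject's paired, unblinded screening and postbaseline photographs", is also collected (Protocol 3, Study Design).

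**The concern.** Masking the order of two photographs works only if nothing in the images gives the order away. Here one image predates the tattoos and the other does not, and a dot lies at the edge of the area being judged. The subject was present when the dots were placed and would know what a visible dot meant. He could then score the pair knowing which image was the later one.

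At stake is the distinction between the blinded SSA, which is coprimary, and the unblinded SSA. If order can be recognised, hope of improvement can enter a score that the hypotheses in Protocol 7.3.1 and SAP 5.1.1.3.2 describe as blinded. A freshly clipped patch of about 1 cm² in the later image would be a stronger cue still.

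**Working it through.** The documents give no sample size, power or alpha figure that bears on this point, so there is no plan figure to reproduce. The check is one of sequence and then of consequence.

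**Sequence**

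1. Screening: global photograph taken and defined as baseline (Protocol 6.1.1.2, 6.4.2).
2. Day 1: two 1-mm dots placed (Protocol 6.4.1).
3. Weeks 24 and 32: dots refreshed if needed, hair parted and combed, pairs presented (Protocol 6.4.2).
4. The subject scores the pair from -3 to +3 (Protocol 7.2).

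Steps 1 and 2 alone establish that only the postbaseline image can show a dot. Step 3 adds less than it seems to. The main verb of the sentence in 6.4.2 concerns presenting the photographs, not taking them. Refreshing before the camera is used is the natural reading, because parting and combing prepare for a photograph, but it is an inference.

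**What would have to be true for order to be recognised**

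- *The dot is visible.* The documents give no image scale. Assume that the photograph covers 150 to 300 mm of scalp and is displayed 100 to 200 mm wide. The scale is then 100/300 = 0.33 to 200/150 = 1.33, and a 1-mm dot appears 0.33 to 1.33 mm wide. Both widths are assumptions, and the range does not show whether a subject would notice the dot.
- *The dot is not masked or cropped.* The readable text is silent. The sentence on presentation in 6.4.2 breaks off, Attachment 12.1 (where the SSA procedure sits) is not shown, and two outside documents are cited. Silence in the public version is not evidence that masking is absent.
- *For the patch, clipping comes before the global photograph.* No readable text gives that order, and the body of 6.4.3 (Macrophotography) is not shown. The patch argument has nothing to rest on.

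**Consequence if order is recognised**

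Let μS and μP be the mean SSA under setipiprant and placebo with order fully masked, and let δ be the shift in score from knowing the order. Subjects are randomised, and under Protocol 5.3 "neither the site personnel nor the subject is aware of which treatment is administered", so take the same δ in both arms. The estimated contrast is

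(μS + δ) − (μP + δ) = μS − μP.

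The shift cancels. The argument for the test is more general. If treatment has no effect, the scores in the two arms come from one distribution, and a cue present in both arms changes that distribution equally. The size of the 2-sided 0.05 test is kept.

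Dilution needs a further mechanism: scores pressed against the upper end of the 7-point scale, or added variance. The documents offer no input for either, so no power loss can be computed.

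The target area hair count, the other coprimary variable, comes from digital analysis of macrophotographs, and the subject does not score it.

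**The case for a change.** The strongest case for a change is that the protocol itself treats masked order as a property worth having. It builds the masking into the coprimary definition, reverses scores to suit it, and collects an unblinded SSA separately. The reference to the vendor manual concerns how photographs are obtained, which need not cover how a blinded pair is prepared for display. Masked order is also a second safeguard: if some subjects guessed their treatment, knowing the order would let that guess reach the score.

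The sequence stands, and so does the fact that the readable text does not say whether dots are masked. The step to a defect does not. The separate instructions are said to cover every aspect of photography, and the second-safeguard argument requires the double blind to fail first, which nothing in the plan suggests.

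The remedies also fare poorly:

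- Taking the global photographs before refreshing the dots leaves any unfaded dot in view. It may also work against the stated purpose of the dots, which is to standardise photography.
- Covering the dot or target area in both images requires the vendor to find the position on a screening image that has no dot. It also hides scalp that the subject is asked to judge. At up to about 1 cm² per target area, two areas would come to about 2 cm².

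**Conclusion.** No change to the plan is needed. The screening image predates the tattoos and the later image does not; this is an ordinary by-product of tattooing only on Day 1. It matters only if a 1-mm dot can be seen at global-photograph scale and is left unmasked. Those are operational details that the protocol assigns to the vendor manual and the separate instructions, and the imaging vendor can settle them when the pairs are prepared.

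Even in the unfavourable case the cue shows order and not arm. The bias in the setipiprant-placebo contrast is zero for a shift common to both arms, and the type I error is unchanged. Some loss of sensitivity is possible but cannot be sized. These conclusions assume that the double blind holds and that expectation acts alike in both arms. They would need another look if the vendor's documents showed visible, unmasked dots together with evidence that subjects could guess their treatment.

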6.4.3 Macrophotography

6.5 Summary of Methods of Data Collection

This study will use eCRFs using remote electronic data capture through a qualified third party vendor. The data will be entered on the eCRFs in a timely manner on an ongoing basis. The investigator is responsible for ensuring that data are properly recorded on each subject's eCRFs and related documents. An investigator who has signed the protocol signature page should personally electronically sign for the eCRFs (as indicated in the eCRFs) to ensure that the observations and findings are recorded on the eCRFs correctly and completely. A certified electronic copy of the eCRFs including data corrections will be provided to the site for archiving at the end of the study.

6.6 Other Study Supplies

The following will be provided by the sponsor:

Modified NHS

The following will be provided by the investigator:

- Sterile pads
- Gloves
- Sphygmomanometer
- Equipment to measure height and body weight
- Equipment (stethoscope, otoscope, etc) to conduct physical examinations
- Internet connection (high-speed connection for eCRF completion and digital image uploads)

The following will be provided by the central laboratory:

- All supplies needed for
- Shipping materials for shipment

The following will be supplied by

- Standardized photography equipment, including the instruction manual
- Equipment for tattoo and shaving

7. Statistical Procedures

[figure not shown]
7.1 Analysis Populations

[figure not shown]
Two analysis populations are defined: modified intent-to-treat (mITT) and safety. The mITT population, consisting of all randomized subjects who have a baseline and at least 1 postbaseline measurement for 1 of the coprimary efficacy measures, will be used for analyses of efficacy data based on the randomized treatment group. The safety population, consisting of all subjects who receive at least 1 dose of study drug (ie, all treated subjects), will be used for analyses of all safety data based on the actual treatment received. All subjects who ingest at least 1 dose of study drug will be included in the safety analysis population included in the summaries of all safety and demographic data. All efficacy variables will be summarized and analyzed using the mITT population.

7.2 Collection and Derivation of Primary and Other Efficacy Assessments

The coprimary efficacy variables will be based on the following 2 measures: TAHC within a 1 cm² circular area on the left side of the scalp and SSA.

- The TAHC is a standardized objective quantification of each subject's number of terminal hairs (hair width $\geq 30~\mu m$) within a 1 cm² target circular area on the left side located at the anterior leading edge of the vertex thinning area of the scalp using digital image analysis.
- The SSA score is the subject's assessment of change of hair growth, scored on a 7-point scale (-3 = greatly decreased, -2 = moderately decreased, -1 = slightly decreased, 0 = remained the same, +1 = slightly increased, +2 = moderately increased, and +3 = greatly increased). The analyses of the SSA from the blinded photograph assessments will be based on the actual change from the screening photographs (ie, if the postbaseline photograph is used as Photo A, the assessment score will be reversed for analyses).

[figure not shown]

[figure not shown]

[figure not shown]
7.2.1 Primary Efficacy Variables

The 2 coprimary efficacy variables are based on the measurements of TAHC and SSA (blinded).

- Change from baseline in TAHC within a 1 cm² target circular area on the left side located at the anterior leading edge of the vertex thinning area of the scalp at Week 24
- Subject Self-Assessment of change from baseline in hair growth as viewed on the subject's paired (before and after presented in a blinded fashion) global photographs of the vertex target area at Week 24 and measured by the distribution of SSA scores

7.3 Hypothesis and Methods of Analysis

Finasteride subjects enrolled prior to protocol Amendment 1 will be summarized alone and will not be included in the analysis models. Hypothesis testing will be 2-tailed with a significance level of 0.05. Comparisons of setipiprant tablets 1000 mg BID versus placebo BID will be made. For all efficacy analyses, no adjustment of significance levels will be made for multiplicity of treatment comparisons.

7.3.1 Primary Efficacy Analyses

[figure not shown]
For analyses of TAHC, the following set of hypotheses will be used to compare setipiprant tablets 1000 mg BID versus placebo BID:

[figure not shown]
- Null hypothesis: There is no difference between setipiprant tablets 1000 mg BID and placebo BID in increasing TAHC (terminal hairs in a 1 cm²circular area) as measured by the change from baseline at Week 24 using digital image analysis.
- Alternative hypothesis: There is a difference between setipiprant tablets 1000 mg BID and placebo BID in increasing TAHC (terminal hairs in a 1 cm² circular area) as measured by the change from baseline at Week 24 using digital image analysis.

For analyses of the SSA, the following set of hypotheses will be used to compare setipiprant tablets 1000 mg BID versus placebo BID:

- Null hypothesis: There is no difference between setipiprant tablets 1000 mg BID and placebo BID in SSA (blinded) of hair growth from baseline at Week 24.
- Alternative hypothesis: There is a difference between setipiprant tablets 1000 mg BID and placebo BID in SSA (blinded) of hair growth from baseline at Week 24.

Change from baseline in TAHC at Week 24 and SSA of the change of hair growth from baseline at Week 24 will be analyzed using an analysis of covariance (ANCOVA) model with treatment as a fixed effect and age and baseline value as covariates (if applicable). The treatment difference (setipiprant tablets 1000 mg BID versus placebo BID) will be constructed based on this ANCOVA model, along with the 2-sided p-value. Finasteride subjects enrolled prior to protocol Amendment 1 will be summarized alone and will not be included in the analysis models.

7.3.3 Safety Analyses

Adverse events will be coded from the verbatim text into preferred term (PT) and primary system organ class (SOC) by using the Medical Dictionary for Regulatory Activities. The number and percent of subjects reporting treatment-emergent AEs at least once regardless of causality will be tabulated. Similarly, treatment-related AEs will be tabulated. The tables will be generated by primary SOC and PT as well as by severity.

[figure not shown]
Safety data will be summarized by frequency distributions or descriptive statistics and described in the detailed analysis plan.

7.4 Other Analyses

Subject disposition, demographic data, and variables relating to the conduct of the study (eg, number of subjects attending each visit) will be summarized overall and by treatment. All data will be listed. The number of subjects enrolled will be summarized, overall and by treatment

7.5 Sample Size Calculation

7.6 Interim Analyses

No interim analyses are planned.

8. Study Visit Schedule and Procedures

Please see Figure 1 for a flow diagram of study design. Table 1 provides the schedule of visits and procedures.

8.1 Subject Entry Procedures

[figure not shown]
8.1.1 Overview of Entry Procedures

Prospective subjects as defined by the criteria in Section 4.3 and Section 4.4 (inclusion/exclusion criteria) will be considered for entry into this study.

8.1.2 Informed Consent and Subject Privacy

The study will be discussed with the subject, and a subject wishing to participate must give informed consent prior to any study-related procedures or change in treatment. The subject must also give authorization and other written documentation in accordance with the relevant country and local privacy requirements (where applicable) prior to any study-related procedures or change in treatment.

Each subject who provides informed consent will be assigned a subject number via the IWRS that will be used on subject documentation throughout the study.

8.3 Procedures for Final Study Entry

A subject is considered to have entered the study once the informed consent form is signed at the time of screening.

8.4 Instructions for the Subjects

Subjects will be instructed to self-administer the setipiprant tablets 1000 mg BID or placebo BID orally with water at least 1 hour before or 2 hours after eating, eg, 1 hour before breakfast in the morning and at least 2 hours after dinner.

In addition, subjects will be required to follow further instructions outlined in Section 4.5.3 and in the procedure manual.

8.5 Unscheduled Visits

If a subject is seen for an unscheduled visit, an assessment and record of AEs should be completed. Additional examinations may be performed as necessary to ensure the safety and well-being of patients during the study. The eCRFs should be completed for each unscheduled visit.

8.6 Compliance With Protocol

At Weeks 24 clinic visits, site personnel will reconcile subject drug usage reports with inspection of wallets (setipiprant or placebo) returned by the subject (ie, numbers of open blisters, unused tablets in any blister, and unopened blisters) in the subject's weekly supplies to document the level of subject compliance with the dosing schedule.

Study drug inventory and accountability records must be kept current and available for review by the clinical site monitor. All used and unused for setipiprant or placebo should remain with their weekly wallet for reconciliation with reported usage (see above). Authorized study personnel, with the monitor's guidance, are responsible to reconcile any discrepancies.

If the subject is noncompliant with the dosing schedule (eg, frequent or lengthy periods of missed doses, overdosing), additional treatment kits will not be dispensed (ie, the subject may be discontinued from study drug treatment at the investigator's discretion after consultation with the sponsor).

